3.2 Secondary Objectives

Aim 2. To identify clinically useful participant characteristics associated with outcome as a way of gaining an understanding of subgroups of participants for whom CBT is most beneficial.

Hypothesis 1: Variables such as treatment motivation at baseline and rapid treatment response will be positively associated with treatment outcome after the acute treatment phase of CBT and through follow-up periods.

Hypothesis 2: Interpersonal distress and extra-intestinal medical problems at baseline will be negatively associated with treatment outcome after the acute treatment phase of CBT and through follow up.

Aim 3. To identify theory-based change mechanisms (active ingredients) that explain how and why CBT achieves therapeutic objectives.

Hypothesis 1: Changes in the severity of IBS symptoms are partly mediated by changes in participants' beliefs regarding the causality (locus of control) and controllability (self efficacy) of IBS symptoms.

Hypothesis 2: Changes in the severity of IBS symptoms are partly mediated by nonspecific factors such as a strong therapeutic alliance and positive expectancy of improvement.

Aim 4. To describe the cost and cost effectiveness of MC-CBT, S-CBT and attention placebo for IBS.

Hypothesis 1: MC-CBT is associated with decreased direct and indirect cost compared to SCBT and associated with increased direct and indirect cost compared to attention control.

Hypothesis 2: MC-CBT will prove cost effective relative to either S-CBT or attention control.

Aim 5. To assess long-term durability of acute treatment effects of CBT at 3-, 6-, 9-, and 12 month follow-ups.

Hypothesis: Participants assigned to both CBT conditions will maintain treatment gains with respect to attention placebo through quarterly follow-up periods extending to 12 months after treatment completion.

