Aims 2 and 3 emphasize identifying baseline participant characteristics that predict response to treatment (hence reflecting moderators of the effects of the interventions) and also identifying time-varying mediators of response to treatment. Response to treatment can be defined in terms of: (1) group differences in an outcome at a given point in time, (2) variation in decay functions after treatment, or (3) variations in change from baseline to the immediate post-test within a given group (i.e. within MC-CBT or within S-CBT). Statistical strategies vary depending on how response to treatment is operationalized.

With respect to mediation, an important facet of mediation analysis is specifying the correct time interval between the change in a mediator and change in the outcome of interest. Changes in a mediator may translate into instantaneous changes in an

outcome or, alternatively, it may take some time before the change in the mediator translates into change in the outcome. If one assesses the mediators after changes have occurred, but measures the outcome *before* the changes in the mediators have manifested themselves in the outcome, one is at risk of misdiagnosing the importance of the mediator. Unfortunately, the time dynamics by which mediator effects translate into outcome effects are not well understood in the IBS area. We will measure our mediators and outcomes at baseline as well as IM, FU3, FU6, FU9 and FU12. We also will measure most of the mediators during treatment, typically every other week, and we will gather a weekly assessment of an outcome proxy, the IBS symptom severity scale. This frequent assessment of mediators and outcomes has the advantage of allowing us to formally explore temporal dynamics with mediators and outcomes within the context of SEM frameworks.

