The richness of the data can be illustrated by considering one example; namely, IBS self efficacy used to predict within-treatment variability in response to outcome at the immediate post-test (IM), pooling the MC-CBT and S-CBT groups to bolster the stability of parameter estimates. IBS self efficacy is measured at baseline (BA) and during weeks 1, 3, 5, 7, 8 and 12 of the acute treatment phase (i.e. W1, W3, W5, W7, W8, W12). There are several plausible mediation models that may bear on results. An *early* response mediation model states that IBS self efficacy gains experienced early in treatment (e.g. from B to W1 and W3) are the primary determinants of the ultimate response to treatment at IM. A recency mediation model states that the level of IBS self efficacy at the last treatment session (W12) is the primary mediator of IM response to treatment. A growth curve mediation model states that it is the general acceleration/deceleration of IBS self efficacy across the acute treatment phase (as well as the shape of the curve) that best predicts response to treatment at IM (with IBS self efficacy being as parameterized as a growth curve per Figure 1). A fourth model is one that incorporates all three types of mediational influence into a single estimating equation, with linear coefficients attached to each to reflect their relative influence in impacting treatment response. The baseline outcome variable is used as a covariate and the IM outcome is used as the criterion. It is possible to use the M Plus software to parameterize all three sources of influences and then test their relative contributions. Note that this can be done to predict response to treatment as measured at IM or it can be used to predict decay functions characterizing change from IM to FU12. Models also can be pursued that include multiple mediators in the same model, thereby permitting complex multivariate explorations of the data.

Aim 4

The following section outlines the steps for the economic analysis of the costs and costeffectiveness of S-CBT and MC-CBT relative to the attention control group.

Aim 4A (Cost Hypothesis): The MC-CBT intervention will have lower costs per person than the S-CBT.

Aim 4B (Cost Hypothesis): Both S-CBT and MC-CBT will be cost-effective relative to the less costly but also less effective attention control. MC-CBT will be at least as effective as S-CBT, and given its lower costs, MC-CBT will be cost-effective relative to S-CBT.

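### Aims 2 and 3 allow moderator and mediator conclusions from change within the CBT arms alone, so prognostic or natural-course associations may be reported as effects or mechanisms of CBT

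*Protocol*

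**What the plan says.** Section 3.2 sets Aim 2 (for whom CBT is most beneficial) and Aim 3 (how and why CBT works). The Aim 2 hypotheses are associations with the outcome of CBT. For example, "rapid treatment response will be positively associated with treatment outcome after the acute treatment phase of CBT".

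Section 7.4, Aims 2 and 3, describes the task as finding characteristics that "predict response to treatment (hence reflecting moderators of the effects of the interventions". It then gives three meanings of response: group differences at a time point, variation in decay functions after treatment, and change "within a given group (i.e. within MC-CBT or within S-CBT". It does not choose between them: "Statistical strategies vary depending on how response to treatment is operationalized".

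The mediation models follow in 7.4 as an illustration: "The richness of the data can be illustrated by considering one example; namely, IBS self efficacy used to predict within-treatment variability". The two CBT arms are combined, "pooling the MC-CBT and S-CBT groups to bolster the stability of parameter estimates", and the baseline outcome is the covariate. No path from treatment to mediator is described. Section 7.3 presents the same early-response, recency and growth-curve models, without mentioning pooling, and commits to fitting all three influences. It adds that moderators will be examined with product terms, but does not say which factor is multiplied by the characteristic.

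**The concern.** A moderator of CBT is a characteristic that changes the difference between CBT and no CBT. Within the CBT arms alone, it cannot be told from a characteristic that predicts recovery under any condition. In the same way, a belief that improves alongside symptoms, or because of them, will correlate with outcome among CBT participants even if CBT never moved that belief.

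Section 8.1 gives separating CBT technique from non-specific therapy effects as the reason for the attention control. Mechanism conclusions drawn without that arm give up the protection it was added to provide.

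Timing adds to the problem. The recency model takes self-efficacy at week 12, which 7.4 calls the last treatment session. Treatment lasts 10 weeks, and 7.3 and 7.4 both place the immediate post-test at week 12. Mediator and outcome are then read at the same visit, and the direction between them cannot be established.

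**Working it through.** **Inputs from the protocol.** 480 participants allocated 1:1:1 give 480/3 = 160 per arm, so 320 pooled CBT and 160 control. The protocol states no power, effect size or correlation for Aims 2 and 3, so there is no figure on this point to reproduce. As a check on the method, the Aim 1 contrast (d = 0.50) was recomputed. It gives 63 per group for 80% power (protocol: about 65, where power is 0.813) and 85 for 90% (protocol: 85).

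**Assumptions.** Two-sided alpha is 0.05. Correlations are r = 0.1, 0.2 and 0.3, read as what remains after adjustment for the baseline outcome.

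**Step 1, closed form.** The power to find a correlation r within n = 320 is Φ(atanh(r) × √(n − 3) − 1.96).
- r = 0.1: 0.1003 × √317 = 1.79, power 0.43.
- r = 0.2: 0.2027 × √317 = 3.61, power 0.95.

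**Step 2, simulation, moderation.** A baseline variable is equally prognostic in all arms, so there is no moderation. There were 2,000 runs per setting.

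| r | Slope within pooled CBT significant | Treatment-by-characteristic term, control included |
|---|---|---|
| 0.1 | 42% | 5.6% |
| 0.2 | 95% | 5.2% |
| 0.3 | 100% | 3.9% |

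**Step 3, simulation, mediation.** Mediator and outcome share a natural course, and treatment has no effect on the mediator. The right-hand column requires both the treatment-to-mediator and the mediator-to-outcome path to be significant.

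| r | Slope within pooled CBT significant | Joint test, control included |
|---|---|---|
| 0.1 | 44% | 3.1% |
| 0.2 | 95% | 3.9% |
| 0.3 | 100% | 4.5% |

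**Step 4, limit of the joint test.** Now let CBT move the mediator by d = 0.3 or 0.5, while the mediator still has no effect on outcome.
- Treatment-to-mediator path: the standard error is √(1/320 + 1/160) = 0.0968. For d = 0.3, z = 3.10 and power is 0.87. For d = 0.5, z = 5.16 and power is about 1.
- Mediator-to-outcome path, n = 480: for r = 0.1, z = 0.1003 × √477 = 2.19 and power is 0.59. For r = 0.2, z = 4.43 and power is 0.99.
- Products for d = 0.3 / 0.5: about 0.52 / 0.59 at r = 0.1, and 0.87 / 0.99 at r = 0.2. Simulation gave 53% / 60% and 88% / 99%.

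Shared natural course therefore still produces false mediation once CBT changes the mediator.

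**Step 5, precision.** The standardised slope detectable with 80% power is (1.96 + 0.8416) × √(1/320) = 0.16 within CBT. The detectable slope difference against control is (1.96 + 0.8416) × √(1/320 + 1/160) = 0.27.

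**The case against.** A reader might infer that Aims 2 and 3 leave out the attention control altogether and that false moderators and mechanisms will be reported. The documents do not support that. The first definition of response in 7.4 is a between-group contrast. The growth model for decay functions, set out under Aim 5, represents all three arms. Section 7.3 plans product terms, and the pooled analysis is presented as one example. Section 8 speaks of characteristics that may predict or moderate outcome, and Aim 3 openly names alliance and expectancy as non-specific mediators. A within-CBT model is also a fair test of the Aim 2 hypotheses as worded, which claim association only. All of this stands, and it limits the point to what the plan permits.

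It does not dispose of the point. The parenthesis in 7.4 asserts an inference that fails under the third definition of response, and no passage makes the between-arm definition the basis for a conclusion. No mediation model with a treatment-to-mediator path is described, and 7.3 commits to fitting the ones that lack it. In a model of the two CBT arms only, a product with treatment could compare MC-CBT with S-CBT but never CBT with control. A separate analysis plan might settle which factor enters the product terms. The complaint, however, concerns what the protocol states, not what it leaves open.

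Two remedies are tempting and unsound. Adding the treatment-to-mediator path does not remove confounding between mediator and outcome, as Step 4 shows. An arm-by-rapid-response term is not evidence of moderation either: section 3.4 defines rapid response by week four, after randomisation, so the arm can affect it.

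**Conclusion.** The point holds in limited form. The protocol allows moderator and mediator conclusions from within-CBT change, equates predictors with moderators under a definition where that is false, and describes mediation models that cannot isolate a CBT mechanism. Prognostic or natural-course associations may therefore be reported as moderators or mechanisms.

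The size, about 43% or 95% against about 3% to 6%, rests on assumed correlations of 0.1 or 0.2, a two-sided alpha of 0.05 and, for mediation, no effect of CBT on the mediator. These are rates of a significant association, which becomes an error only when it is read as moderation or mechanism. The aims are secondary, and no figure stated in the protocol changes.

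**What to change.** - In 7.4, delete the parenthesis in "identifying baseline participant characteristics that predict response to treatment (hence reflecting moderators of the effects of the interventions" that turns predictors into moderators.
- Base any moderator conclusion on a treatment-by-baseline-characteristic product term against the attention control.
- Base any mediator conclusion on a three-arm model with both the treatment-to-mediator and the mediator-to-outcome path, and with the mediator measured before the outcome. The week-12 recency reading does not meet this.
- State that the treatment-to-mediator path is necessary but not sufficient, because mediator-outcome confounding remains if CBT moves the mediator.
- Keep the within-CBT models, including rapid response, but report them as predictors of outcome or as exploratory. Do not use an arm-by-rapid-response term as evidence of moderation.

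The cost is wording and precision. The process measures are already scheduled in the Appendix 7 treatment-period book, which also covers the educational-support arm, so no new data are needed. The detectable standardised slope rises from about 0.16 within CBT to a difference of about 0.27 against control, and some moderator questions will end without a clear answer.

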6.1 Standard CBT (S-CBT)

S-CBT is a skills-based training program ³ that involves 10 weekly, one-hour individual sessions. Treatment is structured around six overlapping phases:

- 1. Information and education regarding stress and its relationship to IBS
- 2. Self-monitoring of stressful situations associated with IBS episodes
- 3. Muscle relaxation exercises both to increase physiological self regulation and to cultivate a sense of mastery or self control over symptoms

- 4. Learning to identify, reevaluate, and change negatively skewed thoughts associated with IBS
- 5. Changing underlying schemas or "core" beliefs (e.g. perfectionism)
- 6. Formal training in problem solving to strengthen the ability to cope more effectively with realistic stressors associated with IBS weekly home exercises are assigned to facilitate skills acquisition.

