6.2 Minimal-Contact CBT (MC-CBT)

MC-CBT covers the same range of procedures featured in S-CBT but relies extensively on self-study materials to facilitate skills building. Additionally, whereas the S-CBT condition involves 10 one-hour clinic visits, MC-CBT meets for only four, one-hour clinic visits over a 10-week period.

- 1. At the first MC-CBT session, treatment is explained, self-study materials are provided and muscle relaxation and self-monitoring are introduced.
- 2. The second treatment session introduces cognitive coping techniques (e.g. decatastrophizing through prediction testing).
- 3. At the third session, participants learn problem-solving techniques and more advanced cognitive coping skills (e.g. modifying core beliefs such as perfectionism).
- 4. The fourth session introduces relapse prevention skills.

In the MC-CBT condition, two 10-minute phone contacts are scheduled at weeks 3 and 7 to troubleshoot around any problems encountered between clinic visits.

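### The pooled mediation example targets within-treatment variability but names no arm term, so a difference between the two CBT arms can be credited to the mediator

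*Protocol*

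**What the plan says.** Section 7.4, under Aims 2 and 3, lists three ways to define response to treatment. One is "group differences in an outcome at a given point in time". Another is "variations in change from baseline to the immediate post-test within a given group (i.e. within MC-CBT or within S-CBT", that is, one arm at a time.

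The section then gives an illustration, introduced with "The richness of the data can be illustrated by considering one example". Its target is "IBS self efficacy used to predict within-treatment variability in response to outcome at the immediate post-test (IM", and its sample is formed by "pooling the MC-CBT and S-CBT groups to bolster the stability of parameter estimates". Self-efficacy is indexed by calendar week, and the early-response version uses gains to weeks 1 and 3. On adjustment the text says: "The baseline outcome variable is used as a covariate and the IM outcome is used as the criterion". No other covariate is mentioned.

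The growth-curve version refers to Figure 1. The Aim 5 text describes that model as having treatment dummy variables with paths to the latent growth factors.

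Section 7.3 describes the same family of models without mentioning pooling, and adds that moderators will be examined with product terms.

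The two pooled arms differ in therapist contact. S-CBT is a programme "that involves 10 weekly, one-hour individual sessions" (section 6.1), while "MC-CBT meets for only four, one-hour clinic visits over a 10-week period" (section 6.2), with short telephone calls at weeks 3 and 7.

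**The concern.** The example states a within-arm target but specifies a pooled model that does not isolate it. Two randomized arms stacked without an arm term give a mediator slope that blends the within-arm association with the difference between arm means.

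Arm could plausibly move both variables. By week 3 an S-CBT participant is due to have had three one-hour sessions, against one session and a ten-minute call in MC-CBT. The predictor built on early gains therefore compares people with unequal therapist contact. If arm also affects outcome by a route other than self-efficacy, that effect is partly assigned to self-efficacy. Aim 3 looks for the active ingredients of CBT, so the risk is that an inert process is named as one. If the two arm differences run in opposite directions, the bias is negative and could hide a real mediator.

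**Working it through.** **Inputs from the protocol.** 160 per arm (section 7.4, Equivalence Testing), so 2 × 160 = 320 in the pooled CBT sample; IBS-SS standard deviation 78; IBS-SS threshold ±50.

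**Assumptions.** dM is the arm difference on the mediator. dY is the arm difference on the outcome by routes other than the mediator. Both are in SD units. The true mediator effect is zero, the baseline–outcome correlation is 0.5, and there is no dropout. The protocol supplies none of these.

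**Check of the inputs.** The protocol states no figure for the mediation models. Its equivalence half-width can be reproduced: 1.96 × 78 × √(2/160) = 17.1, or 17.95 with a 90% assurance factor, against about 18 stated.

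**Bias formula.** In a 1:1 pooled sample without an arm term, the mediator slope is biased by

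(dM × dY / 4) / (1 + dM² / 4)

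- 0.2 and 0.2: 0.010 / 1.010 = 0.010
- 0.3 and 0.3: 0.0225 / 1.0225 = 0.022
- 0.5 and 0.5: 0.0625 / 1.0625 = 0.059

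**From bias to false positives, 0.5 and 0.5 case.** The residual variance is about 0.75 + 0.0625 − 0.0037 = 0.809. The standard error is √(0.809 / (320 × 1.0625)) = 0.0488. The slope is then 0.0588 / 0.0488 = 1.21 standard errors from zero, and P(Z > 1.96 − 1.21) is about 0.23.

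**Simulation.** 4,000 trials per setting, outcome regressed on baseline outcome and mediator, with and without arm (Monte Carlo error at 5%: √(0.05 × 0.95 / 4000) = 0.3 percentage points):

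| dM | dY | Bias, no arm term (formula) | False positives, no arm term | False positives, arm term |
|---|---|---|---|---|
| 0 | 0.5 | 0 | 5.1% | 4.9% |
| 0.5 | 0 | 0 | 5.3% | 5.0% |
| 0.2 | 0.2 | 0.010 | 5.6% | 5.3% |
| 0.3 | 0.3 | 0.022 | 6.9% | 5.0% |
| 0.5 | 0.2 | 0.024 | 7.0% | 4.6% |
| 0.5 | 0.5 | 0.059 | 22.1% | 5.0% |

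**Does the equivalence threshold bear on these differences?** On IBS-SS, 50 / 78 = 0.64 SD. But the protocol requires the whole confidence interval to lie inside ±50. With a half-width of 17.1 to 18, the observed difference must be below about 32 to 33 points (32 / 78 = 0.41 SD). A true 0.5 SD is 39 points, and the standard error is 78 × √(2/160) = 8.7. The chance of declaring equivalence is then P(Z < (32 − 39) / 8.7) = 21%, or P(Z < (32.9 − 39) / 8.7) = 24%.

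**The case against.** Four points on the other side have force.

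*It is one illustration.* A reader might infer that all the mediation models pool the CBT arms without an arm term. The documents do not support that. Pooling appears only in the section 7.4 example, section 7.3 does not mention it, and the Aims 2 and 3 text also allows analyses of group differences. This stands, and the point is limited to the example and to any model fitted to the same pooled sample.

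*Silence is not exclusion.* No sentence rules out an arm term, and a within-treatment target is compatible with pooled estimation that uses arm-specific intercepts. The growth-curve version refers to a figure with treatment dummies. This stands in part. Those dummies act on the growth factors and are not stated to enter the equation for the post-test outcome. Paths from arm to mediator alone leave a direct arm effect to load on the mediator coefficient. The product terms in section 7.3 are for moderators and are not described as arm terms. A full covariate list may properly wait for the SAP, but the protocol itself states the target, the pooling and the single covariate, and these do not fit together.

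*The protocol expects the arms to be alike.* Hypothesis 2 of Aim 1 is that MC-CBT and S-CBT do not differ, and section 6.2 says they cover the same procedures. If that is right, the bias is nil or small. But equality is what the trial tests, so it is a weak ground for leaving arm out.

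*The threshold does not support the larger figures.* A reader might infer that a 0.5 SD difference on both variables is something the protocol would call equivalent, because it is below 0.64 SD. That fails twice. The threshold applies to an outcome, and none is given for self-efficacy. A true outcome difference of 0.5 SD would also be declared equivalent only about 21–24% of the time.

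**Conclusion.** The point holds for the pooled worked example. Its stated target is variation within an arm, and the model it describes does not isolate that variation unless arm is added or the arms are fitted separately. This mismatch does not depend on any assumed effect size.

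The consequence is conditional. A reader might infer that arm differences will be read as mediation; the documents support only that they can be. The arms must differ on both self-efficacy and outcome. Small differences inflate the error rate by one or two percentage points. Only the assumed 0.5 SD on both brings it to about one in five. The size therefore rests on unverifiable arm differences, an assumed baseline correlation and complete data. The comparisons with attention control on the primary endpoint are untouched. This is a free improvement to a secondary-aim analysis.

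**What to change.** In the pooled example in section 7.4, and wherever the section 7.3 models are fitted to pooled CBT arms, state that the treatment-arm indicator enters the equation for the outcome as well as those for the mediator growth factors. Add that an arm-by-mediator term will be checked before a common mediator coefficient is interpreted. If that check indicates different slopes, report the coefficient by arm.

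The pooled sample of 320 is kept, and so is the gain in stability that motivated pooling. The cost is one or two model terms and a negligible loss of degrees of freedom, with no new data.
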